7.3.2.4 Transfusion Independence Rate

Transfusion independence rate is calculated as number of subjects with neither RBC nor platelet transfusion for any period of 8 weeks after the initiation of treatment (or C1D1 visit date for subjects randomized to BSC or randomization for subjects not treated) and up to treatment discontinuation divided by the total number of subjects included in the efficacy analysis. The transfusion independence rate will be compared between the 2 treatment groups using a Cochran Mantel-Haenszel test stratified by the randomization stratification factors at an overall alpha level of 0.05, as further described in Section 7.3.3. In addition, the Mantel-Haenszel weighted difference in transfusion independence rate between the 2 treatment groups and the associated CI will be provided.

The individual RBC and platelet transfusion independence rates will also be presented.

7.3.2.5 Criteria for Response Assessment

The 2003 AML IWG Response Criteria (summarized in Table 1) are used to identify AML subjects with CR, CRp, CRi, or partial response (PR). CRh will also be assessed as a subset of CRi or CRp who have partial hematologic recovery and is defined as <5% of blasts in the bone marrow, no evidence of disease, and partial recovery of peripheral blood counts (platelets $>50,000/\mu$ L and ANC $>500/\mu$ L). Evaluation of response will be conducted by Astex medical monitors assisted by programmed data listings.

Response ^a	Peripheral Blood (PB)	Bone Marrow (BM)
CR	ANC $\geq 1000/\mu$ L, Platelets $\geq 100,000/\mu$ L, independence from RBC and platelet transfusions over the past week, no leukemic blasts ^b	<5% leukemic blasts
CRp	ANC $\geq 1000/\mu$ L, Platelets $< 100,000/\mu$ L, independence from RBC transfusions over the past week, no leukemic blasts ^b	<5% leukemic blasts
CRi	ANC <1000/µL, no leukemic blasts ^b	<5% leukemic blasts
PR	ANC $\geq 1000/\mu$ L, Platelets $\geq 100,000/\mu$ L, no leukemic blasts ^b	Decrease of ≥50% in leukemic blasts to level of 5% to 25%

Table 1:2003 IWG AML Response Criteria

^a Responses are based on both PB and BM conditions.

^b For the purpose of response assessment and according to published IWG criteria, blasts may be seen in PB as rare PB blasts may be identified during regeneration, but the subject is in CR if BM blasts are <5% with no Auer rods (Cheson et al 2003).

ANC=absolute neutrophil count; CR=complete response; CRp=complete response with incomplete platelet recovery; CRi=CR with incomplete blood count recovery; PR=partial response. Source: Cheson et al 2003

Subjects who did not receive any study treatment, or who do not have a valid post-treatment (or post C1D1 visit date for BSC) efficacy assessment (ie, no post-treatment BM/PB sample or the quality of BM/PB sample is not adequate for an assessment of efficacy) will be classified as not evaluable (NE) for response classifications. These subjects will be included in the denominator of the ITT analysis for calculation of response rates. Subjects who cannot be classified into a response category (CR, CRp, CRi, CRh, or PR) or into the NE category will be classified as non-responders (NR) for a given evaluation time point. For subjects who experience different response levels at different visits, the best response in the order of CR, CRp, CRi, and PR will be used for summary and analyses. Subjects who progress (see Section 7.3.2.1 for definition) prior to experiencing a response (CR, CRp, CRi, CRh, or PR) will be included in the NR category. The best response (CR, CRp, CRi, PR, NR, or NE) based on the investigators will be summarized in a table displaying the number and percentage of subjects who meet the criteria for each endpoint. CRh, which is a subcategory of CRp and Cri, will be summarized similarly.

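### The response table leaves marrow-cleared visits with ANC of at least 1000/µL and a recent transfusion without a category, so they default to non-response although the same visit with a lower ANC is a CRi

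*SAP*

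**What the plan says.** SAP Table 1 (Section 7.3.2.5) sets three complete-response categories, all with marrow blasts below 5%:

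- CR: ANC at least 1000/µL, platelets at least 100,000/µL, and "independence from RBC and platelet transfusions over the past week, no leukemic blasts ^b".
- CRp: ANC at least 1000/µL, platelets below 100,000/µL, and "independence from RBC transfusions over the past week, no leukemic blasts ^b".
- CRi: "ANC <1000/µL, no leukemic blasts ^b". There is no platelet or transfusion condition.

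PR needs a fall of at least half in "leukemic blasts to level of 5% to 25" percent, so a cleared marrow cannot be a PR. For CRh the text says "CRh will also be assessed as a subset of CRi or CRp who have partial hematologic recovery", with platelets above 50,000/µL and ANC above 500/µL.

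The default for whatever fits nothing is: "Subjects who cannot be classified into a response category (CR, CRp, CRi, CRh, or PR) or into the NE category will be classified as non-responders". The sentence goes on to limit this to one visit: such subjects "will be classified as non-responders (NR) for a given evaluation time point". Best response across visits is then used, and CRc counts subjects whose best response is CR, CRp or CRi (SAP 7.3.2.7). CR+CRh and CRc are fifth and sixth among the secondary endpoints in the testing order (SAP 7.3.3).

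Protocol Table 6 (Section 9.1) has the same CR, CRp and CRi limits and the same default. It differs on CRh, which it defines as CR with relaxed counts, so that CR's transfusion condition carries over.

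**The concern.** The transfusion condition applies only once ANC reaches 1000/µL. Below that level a cleared marrow is a CRi whether or not the subject was transfused. Above it, an RBC transfusion in the past week removes every category. With all else equal, better neutrophil recovery turns a response into a non-response, and the documents give no reason for this.

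At stake are the CRc rate, its confidence interval and the difference between arms. Time to first response is also affected, because a visit in the gap cannot date a response. RBC need and neutrophil recovery can vary with treatment. In Phase 2, Grade 3 or higher anaemia was 43% on the 10-day and 18% on the 5-day regimen (Protocol Table 3), and G-CSF is part of one comparator regimen (Protocol 7.2). Unequal losses are therefore possible, though nothing in the documents shows that they occur.

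**Working it through.** **No plan figure to reproduce.** The plan's power figures concern OS only. It states no expected CRc rate or power, so the check is of the rules themselves.

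**1. Rules applied to a grid.** Fix marrow blasts below 5% and no leukemic blood blasts. Take ANC 400, 750, 1500/µL; platelets 40,000, 75,000, 150,000/µL; RBC transfusion in the past week yes or no; platelet transfusion yes or no. That gives 3 × 3 × 2 × 2 = 36 cells.

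| ANC | Cells | CR | CRp | CRi | NR |
|---|---|---|---|---|---|
| below 1000 | 24 | 0 | 0 | 24 | 0 |
| at least 1000 | 12 | 1 | 4 | 0 | 7 |

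The 7 NR cells are:

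- all 6 with an RBC transfusion (3 platelet levels × platelet transfusion yes or no);
- 1 with no RBC transfusion, platelets 150,000/µL and a platelet transfusion. This is not CR because of the transfusion and not CRp because platelets are not below 100,000/µL.

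The grid shows which combinations are undefined. It says nothing about how often they occur.

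**2. A matched pair.** Marrow blasts 2%, no blood blasts, platelets 60,000/µL, one RBC unit three days earlier. With ANC 1200/µL this is not CR (platelets), not CRp (RBC transfusion), not CRi (ANC) and not PR (marrow), so NR. With ANC 900/µL it is CRi.

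**3. CRh.** Under the SAP's subset wording none of the 7 gap cells can be CRh. If the count limits were read alone, 5 of the 7 would qualify (those with platelets of 75,000 or 150,000/µL) and would count in CR+CRh but not in the broader CRc. Under Protocol Table 6 none would qualify, because each had a transfusion.

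**4. From visit to subject.** NR is set per visit. Blood is assessed for response on Day 1 of each cycle (SAP 3.1), and where no marrow is taken the most recent one is used (Protocol 11.6.2). One cleared marrow can thus be paired with several blood counts. A subject is lost from CRc only if no visit is ever CR, CRp or CRi.

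**5. Possible size (illustration).** Inputs:

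- About 300 randomized (Protocol 4.1), taken as 150 per arm. One subject is 1/150 = 0.67 points.
- Guadecitabine CRc 16/53 = 30.2% (Protocol Table 2, 10-day regimen).
- TC 21%, the CR+CRi rate in the treatment-choice arm of the Phase 3 trial cited in Protocol 2.1.
- L_G and L_T: percentage of each randomized arm lost through the gap. These are assumed at 0 to 5, since the documents give no value.

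Reported difference = (30.2 − L_G) − (21 − L_T) = 9.2 − (L_G − L_T) points.

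| L_G | L_T | Difference (points) |
|---|---|---|
| 0 | 0 | 9.2 |
| 3 | 3 | 9.2 |
| 3 | 0 | 6.2 |
| 0 | 3 | 12.2 |
| 5 | 0 | 4.2 |
| 0 | 5 | 14.2 |

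Three percent of 150 is 4.5 subjects. With the pooled Phase 2 rate instead (24/103 = 23.3%), the starting difference is 2.3 points, and a 3-point loss in one arm gives −0.7 or 5.3.

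**The case against.** The strongest reply is that little follows in practice. NR holds for one visit only, best response recovers many subjects, and a formal CRc test requires success on OS and five earlier secondary endpoints in a trial whose enrollment stopped for futility. All of that stands. It confines the matter mainly to the reported rates, intervals and response timing.

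A second reply is that classification is not mechanical. The SAP gives it to the sponsor's medical monitors assisted by listings, and bases the best-response table on the investigators. That does not close the gap. No rule is given for the cell, two classifiers are named, neither is blinded (Protocol 6.2), and blinded central review is optional.

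A third reply is that calling every cleared marrow a response redefines an endpoint in an open-label trial, and that incomplete recovery is an odd label for ANC 1200/µL and platelets 120,000/µL. This has weight, and is why both classifications should be reported.

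A reader might also apply an assumed share of affected subjects to the Phase 2 CRc rate and quote the result as the loss. The documents supply no such share. The Phase 2 rate was itself scored under the modified IWG criteria, so any similar loss may already be in it. Whether the published criteria resolve the cell cannot be checked here and is not relied on.

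**Conclusion.** The gap is certain on the text: at ANC of at least 1000/µL, an RBC transfusion in the past week, or a platelet transfusion with platelets of at least 100,000/µL, leaves a cleared-marrow visit as NR, whereas any such visit at a lower ANC is a CRi. CRc can therefore be understated in either arm.

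A reader might infer that these subjects become non-responders outright, or that the CRc rate is wrong. Neither follows. Loss needs the absence of a qualifying response at every other visit, and the number affected and any difference between arms are unknown. Under the assumed one-arm losses of up to 5 points, the illustrative difference of 9.2 points ranges from 4.2 to 14.2; equal loss leaves it at 9.2. OS is untouched. The point deserves correction before lock because response rates will be read whatever the OS result.

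**What to change.** Before database lock, and without reference to treatment arm:

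1. Add one line to SAP Table 1 assigning these visits to CRi: marrow blasts below 5%, no leukemic blood blasts (footnote b retained), and CR or CRp not met because of ANC or a transfusion in the past week.
2. State whether CRh requires transfusion independence, keeping CRh within CRi or CRp. This must be settled together with item 1. Once gap visits are CRi, 5 of the 7 gap cells would meet the SAP's present CRh count limits and enter CR+CRh, while Protocol Table 6 would keep them out.
3. Report CRc under the literal and the exhaustive classification, by arm, with the number of subjects who differ. Name the one used in the hierarchical test.

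Transfusion dates and units are already collected (Protocol 9.1), and the SAP states that it supersedes the protocol's analysis description (SAP 1.0), so an SAP change suffices. The cost is one table line, its programming and one sensitivity table. A few subjects may move from NR to CRi, and comparability with the Phase 2 rates is slightly reduced.

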7.3.2.6 Complete Response and Complete Response with Partial Hematologic Recovery Rates

The CR and CRh rates are calculated individually and combined as the number of subjects who achieve a best response of CR or CRh, divided by the total number of subjects included in the efficacy analysis. The CR, CRh, and combined CR+CRh rates will be compared between the 2 treatment groups using a Cochran Mantel-Haenszel test, stratified by the randomization stratification factors, at an overall alpha level of 0.05, as further described in Section 7.3.3. In addition, the 2-sided 95% CI for the Mantel-Haenszel weighted difference in CR, CRh, and combined CR+CRh rates between the 2 treatment groups will be provided.

7.3.2.7 Composite CR Rate

The CRc rate is calculated as the number of subjects who achieve a best response of CR, CRp, or CRi divided by the total number of subjects included in the efficacy analysis. The CRc rate will be compared between the 2 treatment groups using a Cochran Mantel-Haenszel test, stratified by the randomization stratification factors, at an overall alpha level of 0.05, as further described in Section 7.3.3. In addition, the 2-sided 95% CI for the Mantel-Haenszel weighted difference in CRc rate between the 2 treatment groups will be provided.

7.3.2.8 HCT

The HCT rate will be calculated as the number of subjects who received an HCT after randomization divided by the total number of subjects included in the efficacy analysis. The HCT rate will be compared between the 2 treatment groups using a Cochran Mantel-Haenszel test stratified by the randomization stratification factors, at an overall alpha level of 0.05, as further described in Section 7.3.3. The Mantel-Haenszel weighted difference in HCT rate between the 2 treatment groups and the associated CI will also be provided.

Time-to-stem-cell engraftment is calculated, for subjects who received an HCT after randomization, from the day of transplant to the day of engraftment, as recorded in the CRF. The day of engraftment is the first day of 3 consecutive days of PB absolute neutrophil counts of $>500/\mu$ L. The number and percent of subjects who received HCT and subsequently achieved stem-cell engraftment will be summarized by treatment group. The time-to-stem-cell engraftment will also be summarized by treatment group using mean, standard deviation, median, minimum, and maximum for subjects who have achieved stem-cell engraftment.

In addition, 100-day post-HCT mortality rate (regardless of cause) will be calculated for subjects who received an HCT after randomization and summarized by treatment group. The mortality rate will be number of subjects who died from any cause within 100 days of HCT divided by the total number of subjects who received HCT. HCT subjects who had no survival status data on or after 100 days post HCT will be excluded from the analysis.

7.3.2.9 Duration of Combined CR and CRh

A combined duration of CR and CRh (in number of days) will be calculated from the first time a CR or CRh is observed to the date of the earliest of the following 3 events: (1) relapse (defined as the earliest time point whereby BM assessment or PB assessment by the investigator indicate relapse/disease progression due to confirmed reappearance of leukemic blasts in PB or $\geq 5\%$ leukemic blasts in BM, or clinical progression determined by the investigator), (2) start of alternative therapy (except HCT) or (3) death. In the absence of any event, the combined duration of CR and CRh will be censored at the last available time point (BM assessment, PB assessment, or safety/long-term follow-up visit) at which an event was not observed. Duration of combined CR and CRh will be analyzed using the Kaplan-Meier method for subjects who achieved a CR or CRh during the study and compared between the two treatment groups using a non-stratified log-

rank test. The median and quartiles of duration of complete response, as well as their respective 95% CIs will be provided. Duration of CR will be calculated and analyzed similarly.

To take the proportion of responders into consideration when analyzing duration of combined CR and CRh, a separate analysis including all subjects will be conducted with a 0-day event duration assigned to subjects who did not achieve a CR or CRh. The median and quartiles of duration of complete response, as well as their respective 95% CIs will be provided.

In addition, both time to first response and time to best response will be calculated and analyzed for subjects who achieve a response of CR, CRp, CRi, or PR. Time to first response is defined as the time, in days, from the date of first treatment (C1D1) to the first date when any response is achieved. Time to best response is similarly defined as the time, in days, from the date of first treatment (C1D1) to the first date when a subject's best response, in the order of CR, CRp, CRi, or PR, is achieved. The times to first response and best response will be summarized by treatment group using mean, standard deviation, median, minimum, and maximum. Time to CR will be summarized similarly.

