Laboratory Assessments	Screening ^f (D -14 to -1)					•	•	•						•		•	•		
Hematology ^m	X	X ^m				Х			Х	Х	X ^m						Х	X	Xc
Serum chemistry ⁿ	X	X ⁿ									X ⁿ							Х	
Urinalysis	X																		
Serum or urine pregnancy test ^o	X	Х									Х							Х	
Disease Assessments			1	-	1	1		1	1	1				-	1	1	1		
BM aspirate or biopsy ^r	X	Xr									Xr								Xc
Cytogenetics	X																		
Hospitalizations/Transfusions ^s	X	Х									Х							X	Xc
Subsequent anti-leukemic therapy																		х	Х
Disease progression status ^t																		X	Xc
Survival follow-up																		Х	Х

^a The Day 15 visit is not required after Cycle 6.

Safety follow-up visit: Must occur 30 (+7) calendar days after the last dose of study treatment or before the subject starts another anti-leukemia therapy for AML (except for hydroxyurea as specified in Section 7.4.1), whichever occurs first. If the subject cannot attend the clinic, the visit may be conducted by telephone to collect, at minimum, AE, hospitalizations/transfusions, subsequent anti-leukemic therapy, QOL responses and survival information. Safety follow-up visit may occur at the same time as treatment discontinuation only if decision to permanently discontinue treatment is made at least 30 days after last dose.

^c Long-term follow-up visits: Start after treatment discontinuation. Monthly (±7 days) visits are required for subjects who discontinue study treatment before Cycle 6, until 6 months after the start of study treatment. After monthly visits for at least 6 months, long-term follow-up visits will be every 3 months (±2 weeks) until death. The first long-term follow-up visit should occur 1 month or 3 months (whichever applies) after the safety follow-up visit or after the last dose of study treatment, whichever applies. Monthly and quarterly visits may be conducted by telephone if needed. Refer to Section 9.5.6 for the specific assessments to be performed at the long-term follow-up visits.

Astex Pharmaceuticals, Inc. Clinical Protocol SGI-110-06

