9.5.5 Safety Follow-up Visit

Subjects will attend a safety follow-up visit after study treatment has been permanently discontinued. The safety follow-up visit must occur 30 (+7) calendar days after the last dose of study treatment or before the subject starts another anti-leukemia therapy for AML (except for hydroxyurea as specified in Section 7.4.1), whichever occurs first.

Each subject should be followed, to document the occurrence of any new AEs, for at least 30 (+7) days after his or her last dose of study treatment, or until any AE or SAE assessed as related to study treatment or procedures has resolved to a clinically acceptable or stable resolution (see Section 10.3).

Subjects who withdraw consent should still be encouraged to complete this visit. The following evaluations are to be performed:

- Complete physical examination.
- Vital signs.
- ECOG performance status (Appendix 1).
- 12-lead ECG (triplicate).
- Health-related QOL (Appendix 2).
- All AEs and concomitant medications.
- Sample collection for clinical laboratory tests, including:
 - Hematology (see Table 8)
 - Serum chemistry (see Table 8)

- Serum or urine pregnancy test for women of child-bearing potential only.
- Hospital admission and discharge dates (and the main reason for hospitalization), as well as all blood and platelet transfusions (blood product transfused and units) since they were last recorded.
- Subsequent anti-leukemic therapy (regimen and start date); for HCT, include time to stem cell engraftment.
- Disease progression status: Subjects who discontinue study treatment before documented disease progression must undergo response assessments (PB or BM aspirate/biopsy) until disease progression or relapse is confirmed.

If the subject is not able to attend the clinic for the safety follow-up visit, the visit may be conducted by telephone to collect at minimum AE information, hospitalization information, transfusion information, subsequent anti-leukemic therapy, QOL responses, and survival status. If a decision is made to permanently discontinue study treatment \geq 30 (+7) days after the last dose, then the 30day safety follow-up visit should be performed as soon as possible on the day the discontinuation decision is made or as soon as possible thereafter.

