9.5.6 Long-Term Follow-up

Long-term follow-up starts after subjects discontinue study treatment. Long-term follow-up visits will occur monthly (\pm 7 days) for subjects who discontinue study treatment before Cycle 6, until 6 months after the start of study treatment. After monthly visits for at least 6 months after the start of study treatment, long-term follow-up visits will be every 3 months (\pm 2 weeks) until death. The first long-term follow-up visit should occur 1 month or 3 months (whichever applies) after the safety follow-up visit or after the last dose of study treatment, whichever applies. Long-term follow-up visits may be conducted by telephone if needed.

At the **monthly** long-term follow-up visits, the following assessments are required unless they are refused by the subject. However, at a minimum, information on survival status must be collected.

- Health-related QOL (Appendix 2).
- Hematology and/or BM aspirate/biopsy: Subjects who discontinue study treatment before documented disease progression must undergo response assessments (PB or BM aspirate/biopsy) until disease progression or relapse is confirmed.
- Hospital admission and discharge dates (and the main reason for hospitalization), as well as all blood and platelet transfusions (blood product transfused and units) since the last visit.
- Subsequent anti-leukemic therapy (regimen and start date); for HCT, include time to stem cell engraftment.
- Survival follow-up (must be collected).

At the **quarterly** long-term follow-up visits, the following assessments are required unless they are refused by the subject. However, at a minimum, information on survival status must be collected.

- Health-related QOL (Appendix 2) until disease progression.
- Hematology and/or BM aspirate/biopsy: Subjects who discontinue study treatment before documented disease progression must undergo response assessments (PB or BM aspirate/biopsy) until disease progression or relapse is confirmed.
- Hospital admission and discharge dates (and the main reason for hospitalization), as well as all blood and platelet transfusions (blood product transfused and units) since the last visit until disease progression.
- Subsequent anti-leukemic therapy (regimen and start date); for HCT, include time to stem cell engraftment.
- Survival follow-up (must be collected).

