11.6.2.8 Duration of Combined CR and CRh

Duration of combined CR and CRh (in number of days) will be calculated from the first time a CR or CRh is observed to time of relapse (defined as the earliest time point whereby BM assessment or PB assessment indicate relapse/disease progression due to confirmed reappearance of \geq 5% leukemic blasts in PB or \geq 5% leukemic blasts in BM). The duration of combined CR and CRh will be censored at the last available time point at which a relapse/disease progression was not observed. Duration of combined CR and CRh will be estimated using the Kaplan-Meier method for subjects who achieved a CR or CRh during the study. To take the proportion of responders into consideration when analyzing duration of combined CR and CRh, a separate analysis including all subjects will be conducted with a 0 day event duration assigned to subjects who did not achieve a CR or CRh.

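### Duration of CR+CRh can be censored at a follow-up contact with no blood or marrow sample, which can overstate duration by an unknown amount

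*SAP*

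**What the plan says.** SAP 7.3.2.9 runs the duration from first CR or CRh to the earliest of relapse, start of alternative therapy (except HCT) or death. Relapse means confirmed blasts in PB, at least 5% blasts in BM, or clinical progression as judged by the investigator. Without an event, the duration is "censored at the last available time point (BM assessment, PB assessment, or safety/long-term follow-up visit) at which an event was not observed". The arms are compared among responders by an unstratified log-rank test, and medians and quartiles are reported. Duration of CR follows the same method.

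The protocol's own rule (Section 11.6.2.8) names no visits: the duration "will be censored at the last available time point at which a relapse/disease progression was not observed". SAP Section 1.0 states that the SAP supersedes the protocol's analysis plan, so the SAP rule governs.

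On how visits are held, Protocol 9.5.6 states: "Long-term follow-up visits may be conducted by telephone if needed". The schedule-of-events footnote in 9.5.1 agrees: "Monthly and quarterly visits may be conducted by telephone if needed". At monthly and quarterly long-term visits "the following assessments are required unless they are refused by the subject", followed by: "However, at a minimum, information on survival status must be collected". If a subject cannot come to the safety follow-up visit, Protocol 9.5.5 says "the visit may be conducted by telephone to collect at minimum AE information, hospitalization information, transfusion information, subsequent anti-leukemic therapy, QOL responses, and survival status". That minimum contains no PB, BM or progression status.

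**The concern.** The SAP lists a follow-up visit as a third alternative to a BM or PB assessment, joined by *or*, with no condition that disease status was examined. The restriction to time points without an observed event does not repair this, because blasts cannot be observed in a sample that was not taken.

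The subjects exposed are responders who leave study treatment without relapse. They include those bridged to transplant, who come off study treatment (Protocol 7.4.1) and for whom HCT is not an event. Their recorded duration rests on post-treatment follow-up. If some of that follow-up is by call, they stay at risk in the Kaplan-Meier estimate over time in which the main component of the event is invisible. The estimated duration can then be too long, and the censoring date reflects how contact was made rather than what was known about the disease.

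**Working it through.** No figure in the protocol or SAP depends on this rule, so there is none to reproduce. The check has two parts.

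**1. Can the situation arise under the text?**

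- The SAP accepts a visit alone as a censoring date (7.3.2.9).
- The visit may be a telephone call (Protocol 9.5.1, 9.5.5, 9.5.6).
- At long-term follow-up PB/BM may be refused, and only survival status is compulsory (9.5.6).

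Together these allow censoring at a contact without a sample. As a hypothetical case on the protocol's timetable, take a responder with last dose and last sample at Month 6. The safety visit falls about 30 days later (Month 7), and quarterly contacts follow at Months 10, 13 and 16. If all of these were calls without a blood count, censoring would be at Month 16, and 16 - 6 = 10 months would be unsampled. This needs several consecutive contacts without the required sample.

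**2. How much could it matter?**

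The documents supply none of the inputs, so the following is an illustration by simulation (400,000 responders per scenario). The assumptions are:

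- Relapse is exponential with median 6.0 months, so S(t) = 0.5^(t/6) and S(12) = 0.5^2 = 25%.
- Data cutoff is uniform over 12-30 months after response.
- A fraction *f* of responders moves to telephone-only contact at a time uniform over Months 0-6, independent of relapse.
- A relapse missed for that reason surfaces as death or alternative therapy after a further exponential lag.

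Three rules were applied:

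- **A**, the SAP rule: censor at the last contact; a late death or therapy start is an event on its own date.
- **B**: censor at the last PB/BM assessment, but still count the late event.
- **C**: censor at the last PB/BM assessment and do not count events after the unassessed gap.

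Each cell gives the Kaplan-Meier median in months and the event-free proportion at 12 months.

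| Median lag (months) | *f* | A | B | C |
|---|---|---|---|---|
| 2 | 10% | 6.20; 26.0% | 6.12; 25.0% | 5.99; 24.9% |
| 2 | 30% | 6.69; 28.3% | 6.42; 25.3% | 6.01; 25.1% |
| 4 | 20% | 6.60; 28.9% | 6.34; 26.1% | 5.99; 24.9% |
| 6 | 10% | 6.33; 27.6% | 6.16; 25.8% | 6.00; 25.0% |
| 6 | 30% | 7.16; 32.8% | 6.56; 27.4% | 6.01; 25.0% |

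Against the true 6.0 months, rule A overstates the median by 6.2 - 6.0 = 0.2 to 7.2 - 6.0 = 1.2 months. Rule B leaves 6.1 - 6.0 = 0.1 to 6.6 - 6.0 = 0.6 months, because an unseen relapse is still dated late. Rule C recovers the truth here, but only because the move to telephone contact was assumed independent of relapse.

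**The case against.** The strongest reply is that the protocol designs these visits as disease assessments. Sections 9.5.5 and 9.5.6 and the schedule footnotes require subjects who stop treatment before progression to continue PB or BM assessment until relapse is confirmed, and Table 7 schedules progression status at both visit types. A telephone contact does not remove hematology from the required list, and a local count could accompany it. This stands and limits how often the problem can occur. It does not remove the problem, because Section 9.5.6 places PB/BM among the items a subject may refuse. If every contact was in fact sampled, the narrower rule yields the same censoring dates.

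A reader might infer that relapse is not looked for at all at a telephone visit. That goes too far. A call can reveal death, new therapy or clinical progression, all of which count in the SAP's definition, so a missed relapse may become a late event rather than a censored remission. The safety visit, about 30 days after last dose, can itself add little time.

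A reader might also infer a bias between arms, since guadecitabine is meant to continue while the subject benefits and TC duration follows local practice. The documents do not support this. They give no telephone-visit rate, missed-assessment rate or number of TC cycles among responders, and assessment duties after discontinuation are the same in both arms. Guadecitabine responders also leave treatment, for example for transplant. For the same reason no total of unverified remission time can be calculated.

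The stakes are limited. SAP 7.3.3 keeps the endpoint outside the testing hierarchy as supportive evidence. The responder-only log-rank test compares subsets defined after randomization, so it is not a protected comparison under either rule. In the all-subjects version the median is 0 under both rules if fewer than half respond.

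**Conclusion.** The point holds as a defect in the censoring rule. As written, the rule allows a responder to be censored as relapse-free at a contact where hematologic or marrow relapse could not be detected, and this can overstate the duration of CR+CRh and of CR. The number of responders affected is unknown and is held down by the required sampling until relapse. The shift of 0.2-1.2 months on a true median of 6.0 is conditional on assumed relapse, telephone-contact and lag patterns and is not an estimate for this trial. Neither the size nor the direction of a between-arm effect can be derived from the documents. OS and the tested secondary endpoints do not use this rule. The change is worth making because the remedy is cheap, but it affects a supportive endpoint only.

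**What to change.** In SAP 7.3.2.9, for duration of CR+CRh and duration of CR:

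- Censor subjects without an event at the date of the last PB assessment (count with differential) or BM assessment that shows no relapse. A visit or call without such an assessment does not extend the duration.
- Keep death and alternative therapy (except HCT) as events on their own dates.
- Add a sensitivity analysis that censors at the last adequate assessment when such an event follows two or more missed assessments, and define an adequate and a missed assessment against the protocol schedule.

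The second and third items are needed together. Moving the censoring date alone still counts late deaths and therapy starts after a gap, and so leaves the residual overstatement shown by rule B. The sensitivity analysis addresses that residue, although its two-missed-assessment threshold is milder than rule C.

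The cost is a short text change, a revised censoring-date derivation and one added analysis. PB and BM data are already collected, and SAP Section 6.0 describes the final database lock as still to come. The downside is that reported durations may become slightly shorter.
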